2.3 DURATION OF PARTICIPANT INVOLVEMENT

[figure not shown]
We will screen people with hip fracture who meet the age inclusion criteria. This can take place from the time the patient enters the hospital and up to and including 7 days post –surgery. Once potential participants have been identified they will be followed daily to check the haemoglobin level measured on their blood results. If a haemoglobin measurement triggers inclusion in the study, that is, if the Hb falls to 90 g.L⁻¹ or less, then the patient will be randomised. Randomisation should take place as soon as possible after the triggering haemoglobin measurement and no later than post-operative day 8. This can occur pre-operatively or postoperatively whenever on the patient journey that the Hb value first falls to 90 g.L⁻¹ or less.

Participants who are randomised in the study follow one of two arms: restrictive or liberal blood transfusion. Both arms have the same measurements, data collection and follow up. The participants will be in the study for up to 120 days from entry. Participants will be sent a summary of the study results at the end of the trial by the University of Edinburgh if permission is given to do so. Thereafter there will be no further participant-researcher interactions.

IRAS 299977/308830

Version 5.0 26Jun2024

2.4 PATIENT FLOW THROUGH STUDY

IRAS 299977/308830

Version 5.0 26Jun2024

3 STUDY POPULATION

3.1 NUMBER OF PARTICIPANTS

The sample size calculated for this study is 1126 participants, with 563 in each arm of the study. This allows for a 10% dropout rate and is based on pilot data and expert opinion. We expect an incidence rate for the primary outcome of 15% at 30 days. An absolute risk reduction (ARR) of 5% in the primary outcome is a realistic and meaningful effect size that would change practice (33% Relative RR; Number Needed to Treat, 20).

3.2 RECRUITMENT PERIOD

The total project duration is 69 months.

In month 1-12 we will undertake approvals, set-up, and 10-site internal pilot.

In months 13 - 45 we will set-up the remaining 20 sites; months 25 - 57 will be the main recruitment phase.

In months 58 – 69 we will complete follow-up, analysis, report writing.

3.3 SITE INVOLVEMENT

After an initial 10 site internal pilot 20 further sites will be opened. This should fulfil the target recruitment over 24 months, at a rate of 4 participants/month.

If recruitment falls behind target, then further sites may be invited to join the study: most UK hospitals will be managing people with hip fracture regularly as part of their predictable emergency workload.

3.4 INCLUSION AND RANDOMISATION CRITERIA

Inclusion Criteria

- Adults aged 60 years or over
- Admitted to acute hospital unit for operative management of hip fracture

Randomisation Criteria

• Presence of anaemia (Haemoglobin equal to or less than 90 g.L⁻¹) at any time from admission until the seven days following surgery

3.5 EXCLUSION CRITERIA

- Objection to RBC Transfusion
- Unable to obtain consent (from patient or in accordance with appropriate mental capacity legislation for the site)
- Patient for non-operative management or not expected to survive 48 hours

CR007-T02 v0.5 Page **25** of **69**

IRAS 299977/308830

Version 5.0 26Jun2024

- Patient with a new or suspected acute coronary syndrome meeting 4th Universal Definition(35) during current admission.
- Rapid or uncontrolled blood loss resulting in haemodynamic instability
- Chronic anaemias requiring repeated transfusion (e.g. Myelodysplasia or bone marrow failure syndromes)

3.6 CO-ENROLMENT

Co-enrolment will be permitted if in accordance with ACCORD Co-enrolment Policy (POL008 Co-enrolment Policy) and agreement of relevant CIs.

4 PARTICIPANT SELECTION AND ENROLMENT

4.1 IDENTIFYING PARTICIPANTS AND OVERVIEW OF CONSENT PROCEDURES

Potential participants will be identified by the clinical teams or the local research team (if part of the clinical care team), either in the emergency department or after admission to a hospital ward with a fractured hip. Identification could be through a combination of ward lists, theatre operating lists, trauma MDT meetings, or other sources. Clinical teams and members of the local research team (where they are part of the clinical team) may use information from hospital records to assess eligibility against inclusion and exclusion criteria. Where the clinical team is not part of the research team they will be asked to share information about potentially eligible participants with the research team.

Screening will occur daily from admission until 7 days post-surgery. The potential participant will be approached in person by a member of the clinical team or a member of the research team (where they are a member of the clinical team) to discuss whether they are interested in taking part in the study. Consent will be taken from eligible patients at any point during this period, based on all inclusion/exclusion criteria with the exception of the Hb trigger value (considered "consent in principle" or "pre-consent"), but will only be randomised if their Hb falls to ≤ 90 g.L⁻¹

Where a participant is assessed as lacking capacity (by an appropriately trained member of the research team consulting with the patient's clinical care team where appropriate) the participant's nearest relative/welfare attorney/guardian/consultee will be consulted for advice about what the participant's wishes and feelings would be if they were able to consent for themselves. This is permissible under the provisions of the Adults with Incapacity Act (Scotland) 2000, Mental Capacity Act (England and Wales) and Mental Capacity Act (Northern Ireland) 2016.

A more detailed description of arrangements by UK country is given in section 4.2

IRAS 299977/308830

Version 5.0 26Jun2024

4.2 CONSENTING PARTICIPANTS

4.2.1 Screening

All people admitted with hip fracture will be screened daily for eligibility. A screening log will be maintained at each site which will include data on the numbers of people meeting inclusion criteria for the trial but not entered into the trial along with the reasons for non-enrolment. Recording this information is required to establish an unbiased study population and for reporting according to the CONSORT statement.

4.2.2 Consent

People who are potentially eligible and deemed capable of providing informed consent by the clinical and/or research team will be given a patient information leaflet to read which will fully explain the study with its risks and benefits. A summary sheet and an animated study video (if available) may be provided first to provide a brief outline of the study and allow potential participants to decide whether they wish to proceed before the full PIS is provided. This will then be discussed with them, and consent will be sought by an appropriately trained member of the research team. In patients with visual impairments, this information will be given verbally by a member of the research team. If the participant agrees to enrol in the study, they will be asked to sign the consent form, which will then be countersigned by a member of the research team. Written consent will be sought from the participant wherever possible, but if a participant is unable to write, verbal consent can be taken. Verbal consent must be witnessed by an independent person that is not part of the research team for the study. The participant will be provided with a copy of the consent form, a copy of the form will be filed in the participant's medical notes and a copy filed in the ISF. The informed consent process must be documented in the participant's medical records. Wherever possible, potential participants will be approached as early as possible following admission to provide consent to participate in the trial. This is referred to as "pre-consent" and participants will only be randomised if their haemoglobin concentration decreases to 90g L⁻¹ or less during the period from hospital admission to the seventh day following surgery. This approach will maximise the time available for participants and their nearest relative/guardian/welfare attorney/consultee to decide whether they wish to take part in the trial, prior to developing anaemia and also minimise delays in transfusion once patients become anaemic.

4.2.3 Consent for people without capacity

Some people may be unable to give informed consent because of pain, delirium, or cognitive impairment. This may be temporary, but in the case of people with dementia, loss of capacity may be permanent. Elderly adults with hip fracture are a patient group with a high rate of incapacity both from pre-existing cognitive impairment and/or because of the acute injury. Hip fracture and the associated pain and requirement for analgesia also contribute to a high prevalence of delirium, which can also impair mental capacity. Identification of the contribution of pre-existing and acute incapacity is extremely challenging and may not be possible in a high proportion of cases. However, it is vital to include people with both pre-existing and acute incapacity, or a mixed picture, in the trial to ensure its relevance and generalisability. It is also

CR007-T02 v0.5 Page **27** of **69**

IRAS 299977/308830

Version 5.0 26Jun2024

biologically plausible that the intervention could modify acute incapacity due to delirium, which is an important secondary outcome.

Eligible participants who are assessed as lacking capacity to consent will be enrolled in the study in accordance with the legal requirements of that part of the devolved nations where recruitment is taking place. Consequently, different processes will apply in different UK devolved administrations, and a flow-chart describing this is provided in APPENDIX E.

4.2.3.1 Making decisions for people without capacity in England, Wales, and Northern Ireland

The Mental Capacity Act (Northern Ireland) 2016 is closely aligned with the Mental Capacity Act 2005, which applies in England and Wales. A scheme of mutual recognition of NHS/HSC research ethics committee (REC) review for research involving adults lacking capacity to consent has been agreed between these three nations, therefore for the purposes of the trial, processes used in England and Wales will be used in Northern Ireland.

If there is a person willing and able to take on the responsibilities of Personal Consultee/, a trained member of the research team will describe the trial to the individual and provide them with a Personal Consultee Information Sheet. A summary sheet and an animated video (if available) may be provided first to provide a brief outline of the study and allow the Personal Consultee of potential participants to decide whether they wish to proceed before the full information sheet is provided. It is preferable to seek advice from personal consultees in person but in circumstances where this is not possible, advice can be sought by telephone and a declaration completed in the presence of an independent witness who is not part of the study research team If a declaration is completed over the telephone the personal consultee should be asked to sign the declaration at the earliest opportunity. Recruitment to this study is time critical, therefore if a Personal Consultee is not available to provide advice within an appropriate timeframe (all transfusions should ideally be given within 24 hours, or within 48 hours at the latest) then a suitable independent individual not directly involved in the trial and prepared to act as a Nominated Consultee will be consulted and will be informed about the trial by a member of the research team and given a copy of the Nominated Consultee Information Sheet. If the independent Nominated Consultee agrees, the member of the research team will recruit the patient into the trial. If a patient is randomised into the study via a Nominated Consultee, the Personal Consultee will be informed at the earliest opportunity and their opinion sought about whether the participant would want to continue to take part in the study.

The process will be documented in the patients' clinical notes.

4.2.3.2 Consent for patients without capacity in Scotland

Consent will be obtained in Scotland according to the Adults with Incapacity (Scotland) Act 2000). If there is a Welfare Attorney/Guardian or Nearest Relative an authorised staff member/researcher will describe the trial to the individual in person if possible, or alternatively by telephone or approved video consultation technology if attendance is not possible in a timely manner. The Welfare Attorney/Guardian or Nearest Relative will be provided with a Welfare

IRAS 299977/308830

Version 5.0 26Jun2024

Attorney/Guardian/Nearest Relative Information Sheet or the trial will be described by telephone/video consultation. A summary sheet and an animated video (if available) may be provided first to provide a brief outline of the study and allow the Welfare Attorney/Guardian or Nearest Relative of potential participants to decide whether they wish to proceed and before the full information sheet is provided. If the Welfare Attorney/ Guardian/Nearest Relative agrees, then they will provide consent for inclusion. Direct consent of these individuals will be preferable, however witnessed phone consent will be acceptable, with the individual signing the consent form at the earliest opportunity. Witnesses to consent taken over the telephone/approved video consultation technology must be independent of the study i.e. not part of the study research team. In cases where no Welfare Attorney/Guardian/Nearest Relative is available it will not be legally possible to enrol a patient in Scotland.

4.2.3.3 Procedure if participants regain capacity

Once the participant has recovered from the condition causing incapacity, they will be approached by a member of the research team to obtain permission to continue in the study. The consent to continue process will include assessment and documentation of capacity; providing the PIL and Consent Form for Participant with Recovered Capacity; allowing sufficient time for the participant to understand the material and ask questions; and obtaining written informed consent. Participants with visual impairments will be given the information verbally by a member of the research team. If the participant agrees to continue in the study, they will be asked to sign the consent form, which will then be countersigned by a member of the research team. Written consent will be sought from the participant wherever possible, but if a participant is unable to write, witnessed verbal consent can be taken. Witnesses to verbal consent must be independent i.e. Not part of the study research team. The participant's medical notes and a copy filed in the ISF. The informed consent to continue process must be documented in the participant's medical records.

If the participant is discharged from hospital before regaining capacity, the research team will contact the participant's representative at the 30 and 120 day follow up timepoints to ascertain if capacity has been regained. If it has, the research team will discuss the study with the participant and seek consent from them to continue in the study. If the participant wishes to continue in the study, the research team will post the Recovered Capacity consent form to them, with a stamped addressed envelope for its return.

If the participant declines on-going participation in the study the procedures for withdrawal (below) will be followed. In the rare event that the patient does not regain capacity or staff have been unable to obtain consent to continue, then : In Scotland, the consent from the Welfare Attorney/Guardian or Nearest Relative will continue; In England, Wales and Northern Ireland the advice from the Personal Consultee or Nominated Consultee will continue.

4.2.4 Withdrawal of Study Participants

Participants are free to withdraw from the study **at any point** or a participant can be withdrawn by the Investigator. In Scotland participants can be withdrawn by the Welfare Attorney/Guardian

CR007-T02 v0.5 Page **29** of **69**

IRAS 299977/308830

Version 5.0 26Jun2024

or Nearest Relative who gave consent for the participant to enter the study. In England, Wales and Northern Ireland participants can be withdrawn by the Personal or Nominated Consultee whose advice was sought and who completed a declaration that in their opinion the participant would have no objection to taking part in the study. If withdrawal occurs, the primary reason for withdrawal will be documented in the participant's case report form, if possible.

The participant will have the option of withdrawal from:

- Withdrawal from intervention only permission given to contact participant for follow up questionnaires and to collect information from routine health records for the primary & some secondary outcomes
- 2. Withdrawal from intervention and any on-going aspects of the trial that require participant contact or completion of questionnaires but permission given to collect information from routine health records for the primary & some secondary outcomes
- 3. Withdrawal from all aspects of the trial but continued use of data up to that point

There are no early stopping rules or discontinuation criteria for this study.

4.3 RANDOMISATION

Participants should be randomised as soon as possible after the triggering haemoglobin measurement and no later than post-operative day 8.

Participants will be randomised by remote computer to ensure allocation concealment. Allocation will be in a 1:1 ratio with stratification by centre, age (<80 vs. \geq 80 years) and preexisting diagnosis of cardiovascular disease. Randomisation will be performed using a webbased randomisation system developed by the Edinburgh Clinical Trials Unit (ECTU).

Due to the nature of the intervention blinding of trial participants and local study teams will not be possible, however the primary outcome assessment will be adjudicated by a panel blinded to treatment allocation.

5 STUDY INTERVENTION

5.1 TRANSFUSION THRESHOLD

All eligible people admitted with hip fracture will be approached for this trial and enrolled if consent is given. As part of usual clinical care, all potential participants should have their Hb measured on admission, and usually an additional measurement if required preoperatively, and at least two measurements postoperatively. If an enrolled patient's haemoglobin is Hb 90 g.L⁻¹ OR LESS between admission and the first 7 days following surgery, based on routine clinical care measurements, they will be randomised to either restrictive (Hb 75 g.L⁻¹ OR LESS) or

CR007-T02 v0.5 Page **30** of **69**

IRAS 299977/308830

Version 5.0 26Jun2024

liberal (Hb 90 g.L⁻¹ OR LESS) transfusion strategy. After randomisation they will remain in this transfusion group for the duration of acute hospital stay (or 30 days post-randomisation whichever is shorter). The patient's clinical teams will be informed and made aware that they are in the study and are not blinded to randomisation group allocation.

5.2 STUDY INTERVENTION

5.2.1 Blood Transfusion

Once participants are randomised, the transfusion laboratory at the site will be informed of their treatment allocation by the research team. Where possible the blood transfusion laboratory will add a 'flag' to the participants record to ensure that the treatment arm is recorded, and that blood is released according to the patient's study group. Currently red blood cell transfusions are ordered and released using a combination of paper and electronic requests and this will need to be tailored according to the individual site's processes.

Intervention: liberal transfusion protocol

Participants randomised to the liberal arm will receive one unit of red blood cells as soon as possible after randomisation (ideally within 24 hours) to keep their haemoglobin within the range of 90-110 g. L⁻¹. Participants should receive any subsequent transfusions within 24 hours of an Hb of 90 g.L⁻¹ or less. Transfusions that do not occur or occur > 48 hours post-randomisation will be considered a protocol deviation as detailed in section 13.2.

Comparator: restrictive transfusion protocol

Participants randomised to the restrictive arm will not receive a blood transfusion until their haemoglobin falls to 75 g.L⁻¹ or less and the aim will be to keep their haemoglobin within the range 75-90 g.L⁻¹. Participants should receive a blood transfusion within 24 hours of an Hb of 75 g.L⁻¹ or less. Transfusions that do not occur or occur >48 hours after an Hb of 75 g.L⁻¹ or less will be considered a protocol deviation as detailed in section 13.2.

In all participants these targets apply for the duration of acute hospital admission or 30 days post-randomisation whichever is soonest. Single units of red blood cells will be given, and the haemoglobin rechecked before a further transfusion, unless the responsible clinician decides that multiple red blood cell units are indicated. Situations may arise where a participant has a further haemoglobin measurement **after** the threshold Hb measurement , but **before** a transfusion is given, which alters the requirement to transfuse. In this case, clinicians should use the most recent Hb measurement to determine whether a transfusion is required, the aim being to follow the protocol as closely as possible to keep participants in their allocated Hb range of restricted or liberal.

Acceptable methods of checking haemoglobin include FBC, haemocue or arterial blood gas measurement, depending on local practice, however when point of care testing is used it is recommended that a full blood count is performed as soon as practicable.

IRAS 299977/308830

Version 5.0 26Jun2024

For patients recruited prior to surgery clinicians should follow the protocol as closely as possible in the operating theatre, using point of care haemoglobin measurement.

In the case of life threatening or rapid uncontrolled bleeding e.g., major haemorrhage, or major blood loss in the operating theatre or elsewhere, there can be a temporary suspension of the study protocol and the clinical team may transfuse at physician discretion.

If there are other significant clinical safety concerns related to anaemia in any clinical setting (ward or operating theatre), participants can be transfused before the Hb reaches 75g/L but efforts should be made to maintain Hb within the allocated range.

Any transfusion in circumstances described above should be recorded as a protocol deviation as detailed in section 13.2.

5.2.2 Other study interventions

Participants pre-consented to take part in RESULT-Hip but not yet randomised

All participants enrolled in RESULT-Hip will have their haemoglobin and U&Es (urea and electrolytes) measured as per local practice. This must include a measurement preoperatively and on the first and second postoperative days at a minimum. Additional blood sampling will be at the discretion of the clinical team

Participants randomised to the study intervention (both arms)

All participants randomised to RESULT-Hip will have their haemoglobin and U&Es (urea and electrolytes) measured as per local practice. We would expect participating sites to measure Haemoglobin pre-operatively and, on the first, and second post-operative days as part of routine care.

Haemoglobin and U&Es will be measured at randomisation (baseline) and once more in days 2 - 5. Blood samples for troponin analysis (analysis to take place in Edinburgh, results not available to clinical team) will be taken at randomisation (baseline) and then twice more in days 1 to 5, ideally on the 1st and 3rd calendar days after randomisation with all samples being at least 24h apart from each other. The baseline sample should be taken as soon as possible after randomisation (on the same day and ideally within 4 hours of randomisation). ECGs will be performed at baseline and repeated once in days 2 - 5.

If it is anticipated that the participant will be discharged before Day 3, these assessments should be carried out pre-discharge.

CR007-T02 v0.5 Page **32** of **69**

IRAS 299977/308830

Version 5.0 26Jun2024

Haemoglobin will also be measured as soon as possible after every transfusion given as part of the study (ideally within 24 hours).

Additional blood sampling will be at the discretion of the clinical team unless Haemoglobin is not measured as part of routine care for 5 consecutive days. The protocols for blood sampling and measurement in each study site will be checked and clarified during site set-up.

4AT assessment will be carried out at randomisation, and then twice more in days 1 to 5, ideally on the 1st and 3rd calendar days after randomisation.

EQ-5D-5L will be measured at randomisation, or as soon as practicable after, and at days 30 +/- 7 days and at day 120 +/- 7 days.

Health services utilisation will be measured by questionnaire at 30 +/- 7 days and 120 +/- 7 days.

IRAS 299977/308830

Version 5.0 26Jun2024

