1.4 ENDPOINTS

1.4.1 Primary Endpoint

The primary outcome will be death OR major adverse cardiac events (MACE) OR new myocardial injury after non cardiac surgery (new MINS) within 30 days of randomisation.

MACE will be defined as any combination of the following:

- Myocardial Infarction: Diagnosed using the 4th Universal Definitions for MI(14)
- New Arrhythmia: ECG confirmed arrhythmia resulting in a fall in mean arterial pressure of >20% and requiring pharmacological or cardioversion treatment.
- Cardiac or respiratory arrest: Resuscitation Council UK definitions
- Cardiogenic pulmonary oedema.

New MINS will be defined as : new elevated postoperative troponin above the upper reference limit (URL) with a rise/fall pattern indicative of acute myocardial injury occurring in the first 30 days (and typically within 72 h) after surgery; attributable to a presumed ischemic mechanism,

IRAS 299977/308830

Version 5.0 26Jun2024

clinical symptoms masked by sedation or analgesia in the perioperative setting, ischemic features (e.g. ECG, echocardiographic changes) not required.

To maximize validity and consistency, all participants will have troponin measured at randomisation (baseline), and then twice more in days 1 to 5, ideally on the 1st and 3rd calendar days after randomisation with all samples being at least 24h apart from each other, and 12-lead ECGs will be performed at baseline and repeated once in days 2 - 5. The primary outcome will be determined by an expert adjudication team blinded from group allocation.

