6.3 STORAGE AND ANALYSIS OF SAMPLES

Blood samples for full blood count and urea and electrolytes will be collected at randomisation, then on post randomisation day 3 (window day 2 - 5) and thereafter at the discretion of the clinical team. These will be analysed locally in routine NHS laboratories as part of routine care, and the results recorded in the CRF by the local study team.

The serum troponin measurement will be used to define the primary endpoints and secondary endpoints relating to cardiac complications. Blood will be taken for serum troponin measurement at randomisation, then twice more in days 1 to 5, ideally on the 1st and 3rd calendar days after randomisation with all samples being at least 24h apart from each other. Where possible these will be timed with routine blood sampling as part of normal clinical care. These samples will be drawn by venepuncture (or by arterial or central venous catheter if available) into serum gel. Blood should be allowed to clot for a minimum of 30 minutes then spun as soon as possible, ideally within 2 hours of sample collection. If serum gel is not available at a site, Lithium-Heparin tubes can be used, and separate instructions will be issued for sample processing.

Samples should be labelled and stored at -70C or lower until they are transported to Edinburgh for analysis. Study samples will be shipped from site and stored centrally. Frequency of shipments will be agreed on a per-site basis. Samples will be sent on dry ice to the University of Edinburgh centralised storage When ready for analysis samples will be defrosted at room temperature for 60-120min, mixed well with vortex then centrifuged. Laboratory staff will aliquot 320 μ l from the original tubes to Eppendorf tubes and set in the centrifuge basket before spinning at 3000 G, 6 degrees for 10 minutes.

The ARCHITECTSTAT high-sensitive cardiac troponin I (Troponin) assay (Abbott Laboratories, Abbott Park, IL, USA) will be used for sample analysis in this study and has a limit of detection of 1.2 ng litre⁻¹ and an inter-assay coefficient of variation of <10% at 4.7 ng litre⁻¹. The mean concentration for a healthy reference population is 1.6 (3.1) ng litre⁻¹, and the 99th percentile URL for the whole population is 26 ng litre⁻¹ (females, 16 ng litre⁻¹; 34 males, ng litre⁻¹).

Depending on time, biomarker required and availability of storage, samples will be stored for bona fide research purposes for a period 5 years after the study end date.

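### The baseline troponin may be drawn after the first study transfusion, mainly in the liberal arm, so the apparent reference value for new MINS is not guaranteed to be pre-treatment

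*Protocol*

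**What the plan says.** **Sample timing.** Section 5.2.2 is the most specific rule: "The baseline sample should be taken as soon as possible after randomisation (on the same day and ideally within 4 hours of randomisation". Section 6.3 is looser: "Blood will be taken for serum troponin measurement at randomisation". The schedule in section 6 places the sample on Day 0. Section 7.1 lists troponin among items to be collected at baseline or once available later.

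**Transfusion timing.** Under section 5.2.1 a liberal-arm participant "will receive one unit of red blood cells as soon as possible after" the allocation is made. The same sentence goes on to give the time window and the aim: "ideally within 24 hours) to keep their haemoglobin within the range of 90-110" g/L. For the other arm: "Participants randomised to the restrictive arm will not receive a blood transfusion until their haemoglobin falls to 75" g/L or less; once that happens, "Participants should receive a blood transfusion within 24 hours of an Hb of 75" g/L or less.

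**Entry.** The randomisation criterion in section 3.4 is "Presence of anaemia (Haemoglobin equal to or less than 90" g/L), with no lower bound.

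**Endpoint.** Section 1.4.1 defines new MINS as "new elevated postoperative troponin above the upper reference limit (URL) with a rise/fall pattern indicative of acute myocardial injury", with further conditions. Section 1.4.2 lists the matching secondary endpoint as injury arising after randomisation. Section 6.3 states that the trial troponin serves to define the primary and secondary cardiac endpoints.

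**Blinding.** Under section 4.3, participants and local teams are not blinded. The primary outcome is adjudicated by a blinded panel.

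**The concern.** A baseline should be a pre-treatment value. Here two tasks, the blood sample and the liberal-arm unit, are both to be done promptly from the same starting point, and the protocol does not order them. The sample is drawn by people who already know the allocation.

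New MINS has the highest assumed rate of the three components in section 9.1 (20%, against 10% for MACE and 7% for death). It separates rank 1 from rank 2, and rank 4 from rank 5, in the ordinal outcome of section 9.2. If troponin changes soon after a transfusion, that change would sit inside the reference value more often in one arm than in the other. Blinded adjudicators cannot recover a pre-treatment value that was never drawn.

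**Working it through.** The protocol gives no figure for this point, so the main check sets its rules side by side.

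1. **Order of events.** Sections 1.4.1, 5.2.1, 5.2.2, 6, 6.1, 6.3 and 7.1 fix the sample relative to randomisation and to the other troponin samples (at least 24 hours apart). None fixes it relative to a transfusion. The only firm limit is the day of randomisation.

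2. **Which arm is exposed.** A participant is randomised at Hb 90 g/L or less, which is also the liberal threshold. Every liberal participant is therefore due a unit at randomisation, unless a later Hb result alters the requirement. A restrictive participant is due one at that moment only if Hb is already 75 g/L or less. Section 5.2.1 also allows transfusion for major bleeding or safety concerns. Exposure is therefore possible in both arms and concentrated in the liberal arm.

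3. **Is this sample the reference for new MINS?** Section 1.4.1 names no reference sample, and Appendix A (16.2) defines MINS with no baseline at all. But section 1.4.2 ties new MINS to the period after randomisation, and the Day 0 sample is the only scheduled trial troponin that could show whether an elevation is new. The inference is fair, but the protocol does not state it.

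4. **Illustrative size (assumptions only).** Let *f* be the share of liberal-arm new MINS lost to a late, already raised baseline:
   *f* = (share of liberal baselines drawn after transfusion starts) × (share of new MINS in those participants that is masked).
   - If these are 10% and 25%: 0.10 × 0.25 × 20 = 0.5 percentage points.
   - If they are 30% and 50%: 0.30 × 0.50 × 20 = 3.0 points.
   - So *f* runs from 2.5% to 15%. The protocol supports none of these four inputs.

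5. **Effect on the primary test.** Assume no true effect and 507 per arm (section 9.1). Merge the death ranks and use two possible control splits for none / new MINS / MACE without death / death: 70/20/3/7 and 63/20/10/7. With *a* the restrictive and *b* the liberal distribution:
   - P = Σ bᵢ(Σ_{j>i} aⱼ + aᵢ/2)
   - Var ≈ [(1 − Σ p̄ᵢ³)/12] × (2/n), where p̄ is the average of *a* and *b*
   - z = (P − 0.5)/√Var
   - rejection = 1 − Φ(1.96 − z) + Φ(−1.96 − z)

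   Example, *f* = 10%, first split: *b* = 72/18/3/7.
   - P = 0.4680 + 0.0360 + 0.00255 + 0.00245 = 0.509.
   - Var = (0.6349/12) × (2/507) = 0.000209, so z = 0.009/0.01445 = 0.62.
   - Rejection = 0.0906 + 0.0049 = 0.0955, about 10%.

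| *f* | Spurious difference (points) | Rejection, 70/20/3/7 | Rejection, 63/20/10/7 |
|---|---|---|---|
| 5% | 1 | 6% | 6% |
| 10% | 2 | 10% | 8% |
| 20% | 4 | 24% | 19% |
| 30% | 6 | 48% | 37% |

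The last two rows lie beyond the range in step 4. The table covers masking only. It shows what would follow from a given loss, not that any loss occurs.

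**The case against.** The strongest reply is that the stated ideals already put the sample first in many cases: 4 hours for the sample against 24 hours for the unit, with a protocol deviation only after 48 hours. The transfusion laboratory must also be told the allocation, and blood then requested and released. This stands. A post-transfusion baseline is permitted, not shown to be common, and a reader who infers that most liberal baselines are affected goes beyond the text. But the 4 hours is an ideal and not a requirement, so it does not close the gap.

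A reader might also infer that the problem touches one arm only. It does not: restrictive participants randomised at Hb 75 g/L or less, or transfused for bleeding or safety concerns, can be affected too.

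Nor does the protocol support a known direction of bias. A raised baseline could hide new MINS, but a later fall from it could also satisfy the rise/fall criterion, and two later samples remain. It likewise does not follow that a real early benefit would be hidden: if transfusion prevents injury, no new elevation appears and the participant counts as event-free.

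Section 9.2 plans a sensitivity analysis without atrial fibrillation and new MINS. That would show whether the conclusion depends on new MINS, but it does not repair the primary analysis.

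Finally, the case report form is not shown, and the 48-hour deviation rule already needs transfusion timing. It cannot be said that the times go unrecorded, only that section 7.1 lists neither the sample time nor the transfusion start time.

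**Conclusion.** The point holds as a gap in a stated sampling rule. The baseline troponin follows an unblinded randomisation, nothing places it before the first unit, and the resulting post-transfusion baselines would fall mainly in the liberal arm. The affected component belongs to the primary outcome.

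The conclusion rests on one inference, that this sample is the reference for new MINS, and on one unproven condition, that troponin changes soon after transfusion. Direction and size cannot be determined from the protocol. The 0.5 to 3 point range and the table are illustrations. They should not be read directly against the 5-point target difference, because the primary test works on six ranks. The change is worth making because it removes a route to arm-related bias at little cost, not because bias has been demonstrated.

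**What to change.** - In sections 5.2.2, 6 and 6.3, require the baseline troponin sample after the qualifying Hb and consent but before allocation is revealed, or at the latest before the first post-randomisation transfusion starts. Transfusion timing should not change. Consent in principle before the Hb trigger (sections 4.1 and 4.2.2) makes this workable.
- In section 1.4.1, name this sample as the reference for new MINS, and reconcile Appendix A (16.2) with it.
- Confirm that the sample time and the start time of the first transfusion are recorded.
- Add a sensitivity analysis that flags post-transfusion baselines in both arms, for example by counting them by arm and varying the new MINS status of flagged participants between its possible values. They should not simply be set to missing: that would create missingness concentrated in the liberal arm, whereas section 9.2 imputes under missing at random.

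**Cost.** No extra sample; protocol wording, possibly time fields, and slightly tighter logistics at sites. The rule would apply only to participants enrolled after the amendment, so the trial would contain two baseline rules; the flag lets the analysis show whether that matters.
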